Title: Quadriceps Activation Comparative Analysis Based on Positioning of the Ankle During Supine Straight Leg Raise and Quad Set

Principal Investigator: [name], DPT, SCS, CSCS

Co-Investigators: [name]
[name], MS
[name], BCBA
[name]
[name], BS

Funding Mechanism: State of Florida Grant

Institution(s): Andrews Institute- Rehabilitation
[name]
[name]
[contact]

1 Background / Scientific Rationale

Returning quadriceps neuromuscular control and preventing atrophy is an area of intense current interest in orthopedic rehabilitation and recovery science. It is clear that returning full autonomous control of the quadriceps, including the vastus medialis obliquus (VMO), at full knee extension is an important factor in rehab and dysfunction of the quadriceps leads to a loss of physical performance and self-reported function¹⁻⁴. Quadriceps function is critical for optimal ambulation patterns and eccentric control is essential for the weight acceptance phase of gait^{5,6,7}.

Quadriceps atrophy is one of the most common post-operative side effects of anterior cruciate ligament (ACL) reconstruction, total knee arthroplasty, and many other surgeries including meniscal repairs, patella realignment procedures, and microfracture procedures¹⁻⁴. Due to the swelling within the joint after injury or surgery to the knee, the joint inflammation cascade occurs and leads to the quadriceps being arthrogenically inhibited by spinal neuron inhibition as a protective mechanism⁵. These neural changes usually lead to decreased voluntary quadriceps contraction⁶. Additional contributions of inhibition from post-operative pain, patient apprehension, and surgical procedure requiring protection of the repaired tissue^{5,7,8}. The sooner one regains control of the quadriceps muscles the less atrophy occurs, reductions in strength are minimized, and the more optimal the outcome is achieved for patient recovery⁹.

Studies have shown that neuromuscular electrical stimulation (NMES), Transcutaneous electrical nerve stimulation (TENS), and biofeedback techniques can limit post-operative quadriceps atrophy and can return strength of the quadriceps back to normative values faster than without

those techniques and traditional therapeutic exercise and have better long-term outcomes based on pain, functional outcomes, and return to sport participation rates^{1,7,10-12}.

Irradiation effect is a proprioceptive neuromuscular facilitation technique that causes an overflow of neuronal energy from distal to proximal muscles to increase muscle activity of a targeted muscle^{13,14}. This technique can be used to selectively recruit weaker motor units through the application of resistance or stimulation¹³⁻¹⁵. By inducing a stronger contractile force of the quadriceps, our hope is to return quadriceps function to normal quicker with less atrophy and greater strength^{3,6,12}.

We hypothesize that ankle positioning in maximal dorsiflexion (DF) changes the quantity of contraction as a percent of the reference voluntary contraction when performing a supine straight leg raise compared with having the foot in neutral (0°), relaxed, and plantarflexed (PF) positions. This may help provide insight into proper instruction and cuing for patients to return quadriceps neuromuscular control sooner and thus limiting quadriceps atrophy.

2 Objectives

Aim 1: Determine the effects of ankle positioning on quadriceps neuromuscular activation during supine straight leg raises.

Aim 2: Determine if there is a difference between ankle positioning on quadriceps neuromuscular activation during straight leg raises in supine in healthy versus post-operative participants.

3 Participant Eligibility

All Participants

Inclusion Criteria:

- Males and females ages 18-55

Exclusion Criteria:

- History of diagnosed cancer, neurological disorder, peripheral nerve injury affecting the lower limb or injury to the lower spine with radicular symptoms, which may affect quadriceps activation
- History of musculoskeletal injury to the quadriceps that may affect ability to maintain muscle contractions without excessive fatigue or discomfort

Healthy Controls

Exclusion Criteria:

- Injury to the knee or the quadriceps muscle group within the past 12 months to the tested side
- History of lower extremity orthopedic surgery in the past 12 months to the tested side

Participants with Arthroscopic Knee Surgery

Inclusion Criteria:

- Arthroscopic knee surgery including a meniscectomy, chondroplasty, debridement, loose body removal, and plica excision within the past 28 days
- Scheduled for physical therapy at Andrews Institute Rehabilitation

Exclusion Criteria:

- Multiple ligament reconstruction
- Total joint arthroplasty
- Major surgical complication (infection, deep vein thrombosis, surgical revision, neural impairment/pathology)

4 Participant Enrollment

We intend to enroll 100 volunteers. 50 participants with knee arthroscopy to be tested within the first 28 days after surgery and 50 healthy control participants will be recruited for this study by word of mouth and participants will be screened for inclusion and exclusion criteria. Healthy control participants will be matched by age and leg tested (dominant or non-dominant) with participants in the knee arthroscopy group. Dominant leg will be identified as the leg that the participant uses to kick a soccer ball. Potential participants will have the study described to them including potential risks and will be given the opportunity to read and sign an approved informed consent form. This process will take place prior to any study related activities. If the participant meets inclusion and exclusion criteria, the participant will be scheduled for a testing appointment at the Andrews Research & Education Foundation.

5 Study Design and Procedures

Participants will be screened for all inclusion and exclusion criteria during subject recruitment and will be asked to refrain from heavy lifting, exercise, and any activity that may cause fatigue of the leg muscles 24 hours prior to the testing session. The participants who have undergone knee arthroscopy will be tested on a day they have not done physical activity. The participant's age, date of birth, height, weight, and surgical history (if applicable) will be collected on the Knee History Form (attached), which has been adapted from the 2000 International Knee Documentation Committee Knee History Form, and participants will complete the visual analog scale for pain (VAS).

Participants will have surface electromyography electrodes placed on the skin overlying the vastus medialis oblique (VMO), rectus femoris (RF), vastus lateralis (VL), and tibialis anterior (TA). Electrode locations will be identified through palpation of the muscle belly and electrodes will be placed according to SENIAM recommendations. The identified locations for electrode placement will be shaved, abraded, and cleaned using standard medical alcohol swabs. Subsequent to surface preparation, adhesive Noraxon Single Electrodes, 4cm Ag/AgCl diameter disk shaped, surface electrodes (Noraxon USA, INC, Scottsdale, Arizona) will be attached over the muscle bellies and positioned parallel to muscle fibers using previously published standardized methods.¹⁶ Electrodes will not be replaced or moved throughout the entire data

collection. Electromyographic data will be collected via a Noraxon myoMuscle Ultium EMG (Noraxon USA, INC, Scottsdale, Arizona). Surface EMG data will be visually monitored during the collection of data and sampled.

Following the application of surface electrodes, the reference voluntary contraction normalization method will be utilized so that all surface EMG data can be normalized¹⁶. The reference posture will be a SLR performed to the height of the contralateral knee flexed to 90° with a level to ensure appropriate height is achieved with the moving limb performing max dorsiflexion throughout the motion. Participants will maintain the reference posture for 5 seconds and the middle 3 seconds of the contraction will be selected for data analysis. Two reference voluntary contraction trials will be performed, and the data will be averaged. Participants will be given 30 seconds of rest between each trial. The reference voluntary contraction method was chosen for normalization to account for the knee arthroscopy participants pain and possible weakness¹⁶. Pain and weakness post arthroscopy could hinder obtaining maximal isometric contractions through manual muscle testing. Several studies have shown that within 3 days of knee joint surgery patients can lose up to 80-90% of their quadriceps strength due to a phenomenon called arthrogenic muscle inhibition (AMI) that is in part due to surgical trauma as well as joint effusion^{17,18,19}.

Participants will then have 3 practice repetitions in each position of the foot for a total of 9 repetitions. Upon completion, participants will perform 5 repetitions of SLR and quad sets with the foot in active maximal DF, PF, and a relaxed foot position. In total there will be 15 reps performed. Joint angles will be measured using a goniometer and participants will be instructed to maintain that foot position throughout the motion of the SLR as well as being verbally cued throughout the duration of the task. Video tracking will be used to determine when the motion begins and ends for each repetition. Order of foot positioning and performance of exercises will be randomized. Muscle activation will be recorded for each repetition and 5 repetitions of each foot position will be analyzed. Healthy control participants will perform the exercises on bilateral limbs as will the surgical participants with randomization determining which is done first.

Participants will place the foot in the desire position prior to the quad set and any motion of the leg and will maintain the foot position throughout the motion of the task. The participant will then perform a quad set holding for 1 second, then raise the leg taking approximately 1 second to raise the leg to the height of the contralateral limb with the knee flexed to 90° (based off goniometric measurements), hold for 1 second at the top and lower during the SLR taking approximately 1 second, then continue to hold the quad set for 1 second with the foot in the specified position while the leg is on the table, then relaxing. During the quadriceps set the participant will actively contract their quadriceps for a maximum total of 5 seconds performing 5 repetitions in each foot positioning and the muscle activation will be recorded. The knee will be extended active maximally as is customary with the performance of a quadriceps set and straight leg raise with the participant in the supine position, and remain extended throughout the task. Participants will be asked to maximally contract their quadriceps for the duration of the task as well. There will be a minimum of 1 second duration during both the concentric and eccentric

phases of the movement. Participants will have a minimum of 60 seconds of rest between each repetition.

Before starting each straight leg raise, a rest period of muscle activity will be recorded with the participants ankle in the respective testing position (active maximal DF, PF, and a relaxed foot position). This will allow for the option for the EMG signal to be rectified and adjusted for baseline noise by subtracting the mean of the rectified signal during the quiet period (before the start of each exercise) from the rectified signal.

Analysis will be performed with the first repetition and the last repetition being omitted and the average of the remaining 3 repetitions will be done for each testing position for both controls and intervention groups.

A video camera will be used to record the performance of each exercise. EMG and video acquisition will be synchronized. Each repetition will be sub-divided in 2 phases: concentric phase defined as when the participant works against gravity to actively lift their leg of eccentric phase defined as when the participant works against gravity to slow down the return to the starting point of the concentric phase.

6 Expected Risks and Benefits

Risks and Discomforts:

The risks of this study are minimal but do include quadriceps fatigue and gastrocnemius/soleus as well as tibialis anterior muscle fatigue. To minimize muscle soreness and fatigue, adequate rest breaks will be utilized between sets of contractions. The exercise is strictly designed to keep heart rates normal and measure strength of the quadriceps contraction. The appeal of this exercise regimen is that it is not strenuous and can be used during the first rehabilitation day after surgery while at the same time eliciting changes in quadriceps activation that can be used for proper instruction by therapists and trainers to their patients for optimal rehabilitation. This exercise is designed to keep heart rates in normal exercise ranges. There is a slight risk of temporary skin irritation occurring when the surface EMG electrodes are removed from the skin. The skin may appear to be red after the electrodes are removed.

Benefits:

No direct benefits are expected for the participants involved in the study, however results from the study should help clinicians better understand the current cutting edge in exercise technology.

7 Data Management Procedures

All personal information is strictly confidential and no names will be disclosed except as required by law. Data sheets will have names and identifying information replaced with a participant code to protect the confidentiality of the participant. All information provided by the

participant during this project will be recorded on the appropriate forms and stored in a locked room in the Andrews Research & Education Foundation (AREF) research facility. In addition, all participant data forms will be scanned and stored, along with summary information forms, spreadsheets, and photos, in a secure password protected folder on a laptop in which only study investigators will have access to and will be permanently deleted following any and all publications or presentations have been completed related to this research. All records related to this research will be retained in a secure location for a period of 3 years following the completion of all study related activities, at which time they will be properly destroyed.

8 Data Analysis

Data will be analyzed using custom-built MATLAB Software. Rectified EMG will be smoothed and filtered according to standard procedures for human surface EMG. Root mean square values will be calculated and normalized to the reference voluntary contraction. Root mean square values will be calculated for each repetition of the SLR and for each of the three phases (isometric, concentric, and eccentric) and across the whole trial. Processed data will be exported to Microsoft Excel and SPSS.

9 Statistical Considerations

Statistical analysis will be performed in excel and SAS Studio (Version 3.8 on SAS 9.4, SAS Institute Inc., Cary, NC). A 2 (group) x 4 (position) x 3 (phase) MANOVA will be performed for each muscle and appropriate post-hoc tests will be used to ascertain differences among variables. The alpha level will be set *a priori* at $p < .05$.

10 Quality Control and Assurance

All protocols will be monitored and analyzed data will be checked for accuracy by the principal investigator and/or a designated research team member. All medical data will be kept in compliance with HIPAA guidelines.

11 Regulatory Requirements

Informed Consent:

The informed consent process will be performed by one of the study investigators or staff. All participants will have the study described to them and will be given as much time as they would like to read an approved, stamped version of the informed consent document. After signing the informed consent document, they will be given a copy for their records. This process will take place at the AREF.

Participant Confidentiality:

Participant confidentiality information is listed above in #7 (Data Management Procedures). All medical data will be recorded and stored in compliance with HIPAA guidelines.

Quadriceps Activation Comparative Analysis Based on Positioning of the Ankle during Supine Straight

Leg Raise.

[name] DPT, SCS, CSCS

Page 7 of 9

12 References

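### Controls are matched to surgical patients on age and tested leg but not on sex, so an unequal sex mix could enter the Aim 2 comparison; adding sex to the matching rule is a cheap improvement

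*Protocol*

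**What the plan says.** Aim 2 in Section 2 is to "Determine if there is a difference between ankle positioning on quadriceps neuromuscular activation during straight leg raises in supine in healthy versus post-operative participants". Group membership is observed, not assigned. Section 4 plans "50 participants with knee arthroscopy to be tested within the first 28 days after surgery and 50 healthy control participants", and its rule for choosing controls is: "Healthy control participants will be matched by age and leg tested (dominant or non-dominant) with participants in the knee arthroscopy group". Section 3 admits "Males and females ages 18-55" without restricting or stratifying by sex in either group.

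For baseline data, Section 5 states: "The participant's age, date of birth, height, weight, and surgical history (if applicable) will be collected on the Knee History Form". Height and weight are therefore available, but sex is not in that list. The form itself is described as attached and is not shown, so it may hold a field for sex.

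Section 9 names the analysis: "A 2 (group) x 4 (position) x 3 (phase) MANOVA will be performed for each muscle". Its terms are group, position and phase. Sections 5 and 7 provide that RMS EMG is normalised to each participant's own reference contraction, a straight leg raise held in maximal dorsiflexion.

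**The concern.** When groups are not randomised, control of composition rests on whom the study recruits and on what the analysis adjusts for. By matching on age and leg, the protocol accepts that composition matters, but it leaves out sex, which is easy to match. Surgical patients must be scheduled for therapy at one institute, whereas healthy controls are recruited by word of mouth. Nothing in the plan makes the sex mix of the two groups alike.

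The group-by-position comparison answers Aim 2. If men and women respond differently to foot position, and the groups differ in their share of men, part of that comparison reflects who was enrolled rather than the surgery. The effect could go either way, creating a difference or hiding one. The same reasoning applies to body size.

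Timing matters. Adjustment can be added in a later analysis plan, but matching happens at enrolment and cannot be restored afterwards. Adjustment for sex also needs sex to have been recorded.

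**Working it through.** **Inputs from the protocol.** Group sizes are 50 and 50, and 50 + 50 = 100 agrees with the stated enrolment. Alpha is 0.05; the protocol does not state sidedness, so two-sided is assumed. It gives no SD, effect size or power calculation, so there is no design figure to reproduce beyond the total.

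**Assumed inputs (none is in the documents).**
- d: difference between the sexes in the within-person position contrast, in SD units of that contrast. Range 0 to 0.8.
- g: difference between the groups in the share of men. Range 0.20 to 0.30.

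**Formulas.**
- Bias in the group difference of the position contrast = g × d.
- Standard error = sqrt(1/50 + 1/50) = sqrt(0.04) = 0.20 SD.
- With s = bias / 0.20, the rejection rate when surgery has no effect = Φ(−1.96 − s) + 1 − Φ(1.96 − s).

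**Results.**

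| d (SD) | g = 0.20: bias, rejection | g = 0.30: bias, rejection |
|---|---|---|
| 0 | 0, 5.0% | 0, 5.0% |
| 0.2 | 0.04, 5.5% | 0.06, 6.0% |
| 0.5 | 0.10, 7.9% | 0.15, 11.7% |
| 0.8 | 0.16, 12.6% | 0.24, 22.4% |

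Worked corner: 0.30 × 0.8 = 0.24 SD, so s = 0.24 / 0.20 = 1.2. Then Φ(−3.16) + 1 − Φ(0.76) = 0.001 + 0.224, or 22.4% before rounding the parts.

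**Does normalisation already deal with this?** A simulation of the normalised outcome (4,000 runs per setting, assumed 70% men in one group and 40% in the other, no surgery effect) separates two cases.
- Sex changes EMG amplitude only: the test rejects in 5.4% of runs. The simulation error is about sqrt(0.05 × 0.95 / 4000) = 0.3 points, so this is close to nominal. Normalisation works here.
- Sex changes the position response by 0.10 or 0.15 of the reference value: the expected spurious difference is 0.30 × 0.10 = 0.030 or 0.30 × 0.15 = 0.045 (simulated 0.031 and 0.045 in size). The test rejects in 10.4% and 17.1% of runs. With sex in the model, the rates are 4.8% and 4.6%.

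Normalisation therefore covers the first case and not the second. Recording and using sex covers the second. No calculation was made for body size; the formula has the same form, but the documents give no input for it.

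**The case against.** The strongest reply is that the design already protects itself. Each value is divided by the person's own dorsiflexed leg raise, and position is compared within the person. This stands, and it limits the point to a position response that itself varies by sex or size. A reader might infer that heavier limbs alone would distort Aim 2. The documents do not support that: the reference contraction raises the same limb to the same target height, so much of the limb load is in the denominator.

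The second reply is that both d and g are assumed. This also stands. The range starts near nominal, and the 22% needs both upper values together.

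Third, a reader might argue that groups of 50 left unmatched on sex will often differ by chance, and take that as evidence of confounding. It is not. Chance imbalance from a common population is already reflected in the standard error, and the type I error over all such trials stays at 5%. Only a systematic difference in composition produces bias. Differing recruitment sources make one possible, but no passage shows one, and the word-of-mouth sentence can be read as covering both groups.

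Fourth, covariates are commonly left to the analysis plan, which is not at hand. A reader might call their absence from Section 9 an error; that goes too far. The matching rule, however, is fixed in the protocol.

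Finally, a reader might treat the group comparison as the only evidence on surgery. Section 5 has both limbs exercised in both groups, so a comparison of operated with other limb within patients is possible from the data, although Section 9 names no limb factor.

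**Conclusion.** The point holds as a cheap improvement for Aim 2 only. The protocol matches on two factors, omits sex although both sexes enrol, and does not list sex among the data collected. This is an incomplete design choice, neither a contradiction nor a misstatement.

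Its size cannot be determined from the documents. The bias is zero if the position response does not vary by sex or body size, or if the groups have the same composition. Under assumed sex gaps of 20 to 30 points and assumed sex differences of 0.2 to 0.8 SD, with 50 per group and a two-sided 5% test, the rejection rate with no true group difference is about 5.5% to 22%. A reader might conclude that Aim 2 is confounded as planned; the documents show only that it could be. Aim 1 compares positions within the person and is not affected.

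**What to change.** In Section 4, add sex to the matching factors. In Section 5, add sex to the data recorded on the Knee History Form, unless the form already holds it. With each control of the same sex as the matched patient, the sex gap is zero and so is the bias from it.

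As a secondary step, which may sit in the analysis plan, adjust the Aim 2 group-by-position contrast for sex, and for body size from the height and weight already collected. In a repeated-measures model this means sex-by-position and body-size-by-position terms, because main effects alone would not act on the contrast. Report sex and body size by group so that readers can judge the balance.

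The cost is one matching factor, one field on the form if it is not there, and a few model terms. The downside is a slightly narrower pool of eligible controls. For any controls already enrolled, matching may no longer be possible; recording sex and adjusting for it would then be the remedy.

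### Controls are matched on age and leg tested, but the Section 9 model carries neither the matching nor the limb compared; the cost is a conservative group main effect, and only if age or leg predicts normalised EMG

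*Protocol*

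**What the plan says.** Section 4 (Participant Enrollment) plans "50 participants with knee arthroscopy to be tested within the first 28 days after surgery and 50 healthy control participants" and adds that "Healthy control participants will be matched by age and leg tested (dominant or non-dominant) with participants in the knee arthroscopy group". It does not give the age tolerance, or say whether matching is one-to-one or by frequency.

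Section 5 (Study Design and Procedures) then has both legs tested in both groups: "Healthy control participants will perform the exercises on bilateral limbs as will the surgical participants with randomization determining which is done first".

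Section 9 (Statistical Considerations) names one model: "A 2 (group) x 4 (position) x 3 (phase) MANOVA will be performed for each muscle", with unspecified post-hoc tests and alpha 0.05. Its factors are group, position and phase. Age, leg dominance, matched set and limb are all absent.

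The aim that involves the groups is Aim 2 in Section 2: "Determine if there is a difference between ankle positioning on quadriceps neuromuscular activation during straight leg raises in supine in healthy versus post-operative participants".

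**The concern.** Matching is a design feature, and the stated model ignores it. Matching on a factor that predicts the outcome makes the two groups' results positively correlated. A model that treats the groups as independent then assigns the group difference a larger variance than it has. The matching still gives balance, but the precision it could have given is thrown away. Eligibility is wide in age ("Males and females ages 18-55"), so a relation between age and activation is at least possible.

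The leg match raises a second question. Section 4 matches on the leg tested as if there were one per person, Section 5 records two, and Section 9 has no limb factor. Nothing fixes which control leg stands against the operated leg, so the leg match has no defined role in the analysis.

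**Working it through.** **Inputs.** From the protocol: 50 per group (Section 4) and alpha 0.05 (Section 9; two-sided assumed). The protocol gives no power, effect size, SD or within-pair correlation, so there is no planned figure to reproduce. Assumed: one-to-one pairs, and a within-pair correlation r from 0 to 0.3.

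**Reference effect.** For unmatched groups, the standardised difference detectable with 80% power is d = (1.96 + 0.84) x sqrt(2/50) = 2.80 x 0.20 = 0.56.

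**Group main effect.** With outcome SD s:

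- standard error used by the model: s x sqrt(2/50)
- true standard error under matching: s x sqrt(2(1 - r)/50)
- overstatement: 1/sqrt(1 - r) - 1
- actual type I error: 2 x [1 - Φ(1.96/sqrt(1 - r))]
- power ignoring the matching: Φ((2.80 - 1.96)/sqrt(1 - r))
- power using the matching: Φ(2.80/sqrt(1 - r) - 1.96)

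| r | SE too large by | actual type I error | power, matching ignored | power, matching used |
|---|---|---|---|---|
| 0 | 0% | 0.050 | 0.80 | 0.80 |
| 0.1 | 5.4% | 0.039 | 0.81 | 0.84 |
| 0.2 | 11.8% | 0.028 | 0.83 | 0.88 |
| 0.3 | 19.5% | 0.019 | 0.84 | 0.92 |

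At the same r, using the matching gains about 3 points of power at r = 0.1 and about 8 at r = 0.3. The formulas are normal approximations. A paired analysis has 49 error degrees of freedom instead of 98, which moves the critical t from 1.984 to 2.010, a factor of 1.013. Pairing therefore narrows the interval once r exceeds about 1 - 1/1.013² = 0.03.

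**Group x position (Aim 2).** Write a participant's value at a position as level + position effect + noise. A difference between two positions removes the level, and with it any age or leg effect that is the same at both positions. The correlation that matters is then that of the within-person differences. It is zero unless age or leg changes the position effect.

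**Simulation check.** 50 age-matched pairs, two positions, 20,000 replicates. Age explains a share of the between-person variance in level only, and within-person noise has SD 0.5 of the between-person SD. The unpaired test gave:

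| share explained by age | main effect: model SE / true SE | main effect: type I error | group x position: model SE / true SE | group x position: type I error |
|---|---|---|---|---|
| 0 | 1.01 | 0.049 | 1.00 | 0.049 |
| 10% | 1.05 | 0.039 | 1.01 | 0.047 |
| 20% | 1.10 | 0.031 | 1.00 | 0.048 |
| 30% | 1.17 | 0.023 | 1.00 | 0.049 |

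The main effect behaves as the formulas predict. The interaction contrast loses nothing when age acts on level alone.

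**The case against.** The strongest reply is that no stated aim depends on the quantity affected. Aim 1 compares positions within a person. Aim 2 asks whether the position effect differs between groups, which is a contrast of within-person differences. This largely stands. A reader might infer that the model gives Aim 2 the wrong variance and too wide an interval. The protocol does not support that, because it says nothing to show that age or leg modifies the position effect.

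Second, r may be close to zero. Section 5 normalises each value to the participant's own straight leg raise in maximal dorsiflexion, which may remove much of any age-related difference in level. This is an inference, but a fair one, and r = 0 belongs in the range. The same step leaves the cancellation for Aim 2 unproven: the reference posture uses one of the tested foot positions, so the age effects that remain may differ by position.

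Third, the direction is benign. Ignoring the pairs neither biases the group difference nor increases false positives, and balance is a legitimate reason to match in a non-randomised comparison. This stands.

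Fourth, equal group sizes also fit frequency matching, for which a pair term would be out of place. This stands too, and it makes covariates the safer remedy.

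Last, covariates are often left to the SAP, which is not at hand, and matching by leg tested may already imply legs of the same dominance. But Section 9 does fix a model and its factors, and they omit what Section 4 builds in. With both legs recorded, the implication needs to be written down.

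**Conclusion.** The mismatch between design and model is real: controls are matched on two factors, and neither those factors nor the matched set appears in the only model stated. The limb for the group comparison is also not fixed. The consequence is modest and conditional. For r from 0 to 0.3, the standard error of the group main effect is overstated by 0 to 20%, always in the conservative direction. The range for r is an assumption, and the figures rest on one-to-one pairing, which equal numbers suggest but the protocol does not state.

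Two further readings are tempting. One is that the standard error is wrong whatever the data show; at r = 0 it is right. The other is that power rises from 80% to as much as 92%. That sets the matched analysis at r = 0.3 against the unmatched one at r = 0, whereas at r = 0.3 the unmatched analysis already has 0.84.

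**What to change.** In Section 9, include age (continuous) and leg dominance as covariates, with their interactions with position for the Aim 2 test. If matching is one-to-one, the alternative is a matched-pair effect in a repeated-measures mixed model. State in Section 4 which type of matching is used and how close in age. State in Section 9 that the operated leg is compared with the control's leg of the same dominance.

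No new data are needed: Section 5 records age, and dominance must be known to carry out the matching. For the group main effect, the two covariates reduce the between-subject error degrees of freedom from 98 to 96; the position interactions cost a few more in the Aim 2 test. The pair effect costs more: a pair identifier, a change from MANOVA to a mixed model, and about half the between-subject error degrees of freedom (98 to 49).
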